2.2 Study Design

2.2.1 Overview

This study is a multisite, placebo-controlled, double-blind, randomized Phase 3 study to evaluate the efficacy, safety, and tolerability of obicetrapib in participants with underlying HeFH and/or a history of ASCVD who are not adequately controlled by their lipid-modifying therapy.

Approximately 2400 eligible participants will be randomized in a 2:1 ratio, respectively, to the following treatment groups:

- Obicetrapib group: one 10 mg obicetrapib tablet once daily; or
- Placebo group: 1 placebo tablet once daily.

Treatment allocation will be stratified based on CV risk (HeFH or non-HeFH) and Baseline statin dose (high-intensity statins [HIS] or non-HIS). At least 70% of the participants enrolled into this study must be taking HISs. Participants with underlying HeFH but without a history of ASCVD will comprise up to a maximum of 20% of the total participants enrolled into the study. Starting on Day 1, each participant will self-administer their assigned study drug once daily until Day 365. During the Treatment Period, participants will return to the study site for efficacy and safety assessments. Blood samples for pharmacokinetic (PK) assessment will be collected at specified visits throughout the study. Participants will return to the site for the End Of Study (EOS) Visit (Visit 8) approximately 35 days after last dose of study drug for safety assessments.

A subset of approximately 200 participants from selected study sites who consent to participate will be enrolled in an ambulatory blood pressure monitoring (ABPM) substudy. These participants will have a 24-hour ABPM assessment conducted at Screening (Visit 1) and Visit 6 (Day 270). In order to participate in the substudy, participants must provide written informed consent in a substudy-specific informed consent form (ICF) and must be able to provide an acceptable 24-hour ABPM data collection at Screening (Visit 1).

The study drug blind will be maintained through the EOS Visit (Visit 8). Participants, the Sponsor, Investigators, and all study site personnel involved in the study, including personnel carrying out study procedures, evaluating participants, entering study data, and/or evaluating study data, will

remain blinded to treatment allocations until all participants have completed the EOS Visit assessments and the database has been locked for analysis.

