18. A PK sample will be collected prior to study drug administration for trough measurement of obicetrapib in plasma. At Visits 2, 5, and 7, participants should take study drug after a trough PK sample has been drawn.
19. CV events include CV death, non-fatal myocardial infarction, non-fatal stroke, non-elective coronary revascularization, hospitalization for unstable angina and/or chest pain, hospitalization for heart failure, and transient ischemic attack.
20. The PK sample at Visit 4 is not designated in the protocol, however the PK will be assessed using residual serum from the Day 84 limited chemistry panel to confirm participants are taking study drug.

ABPM = ambulatory blood pressure monitoring; AE = adverse event; ApoA1 = apolipoprotein A1; BMI = body mass index; CV = cardiovascular; ECG = electrocardiogram; EOS = End of Study; EOT = End of Treatment; ET = Early Termination; FSH = follicle-stimulating hormone; HOMA-IR = homeostatic model

assessment of insulin resistance; hsCRP = high sensitivity C-reactive protein; ICF = informed consent form; Lp(a) = lipoprotein (a); PK = pharmacokinetic(s); TSH = thyroid-stimulating hormone; UACR = urine albumin-creatinine ratio; UPCR = urine protein-creatinine ratio; V = Visit.

2.2.2 *Sample Size Determination*

Enrollment of approximately 2400 participants globally is planned for this study.

Assuming an approximate 5% drop out rate, approximately 2280 participants will be evaluable for efficacy. This sample size of at least 2280 evaluable participants will provide more than 90% power to detect a 30% reduction of LDL-C (standard deviation 15%) levels in the obicetrapib group compared to the placebo group at a 1-sided significance level of 0.025. This sample size will also contribute to sufficient participant exposure and safety data.

ABPM substudy

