3.4.1 Primary Efficacy Endpoints

Primary Analysis

The primary efficacy endpoint is the percentage change from Baseline to Day 84 in LDL-C in the obicetrapib group compared to placebo group.

The LDL-C values measured by preparative ultracentrifugation (PUC) will be used. If the later is not available, the LDL-C values will be assumed missing.

All the analysis for primary efficacy endpoint will be repeated with LDL-C values calculated as follows:

1. LDL-C will be calculated using the Friedewald equation unless triglycerides ≥ 400 mg/dL or LDL-C ≤ 50 mg/dL; where, LDL-C level will be measured directly by PUC.
2. LDL-C will be calculated using the Martin-Hopkins equation unless triglycerides ≥ 400 mg/dL or LDL-C ≤ 50 mg/dL; where, LDL-C level will be measured directly by PUC.

Primary Estimand

To assess the primary efficacy endpoint, the primary estimand is defined by the following key attributes:

- **Treatment:** obicetrapib versus placebo
- **Target Population:** participants who are randomized into the study
- **Analysis Population:** The ITT Population
- **Intercurrent events:** treatment discontinuation, prohibited medication use
- **Analysis set and handling of intercurrent events:** Treatment policy strategy will be used. All available values of LDL-C at Baseline and Day 84 will be included in the calculation of the percentage change from Baseline to Day 84.
- **Population level summary:** The difference in LS mean percentage change in LDL-C from Baseline to Day 84 between treatment groups

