The analysis of covariance (ANCOVA) model with a fixed effect for the treatment group and covariates of Baseline LDL-C, CV risk (HeFH or non-HeFH), and Baseline statin therapy (HIS or non-HIS) will be used to analyze the primary efficacy endpoint. The CV risk and Baseline statin therapy covariates, that were used in the stratification of the randomization scheme, will be classified according to the IRT stratification levels (meaning, the stratification categorization at the time of the randomization). The least squares (LS) mean, standard errors, and 2-sided 95% confidence intervals for each treatment group and for the mean difference compared to placebo will be estimated. The model will be fit assuming unequal variances for each treatment group. If substantial deviations from the model assumptions are observed, then supportive analyses, such as non-parametric assessments, will be considered. The primary efficacy analysis will be conducted based on the ITT Population.

Missing data will be imputed for the primary efficacy analysis based on a pattern mixture model that uses a multiple imputation technique analyzed with ANCOVA with pre-specified fixed factors and covariates. If appropriate, based on the number of retrieved dropouts, missing measurements of non-retrieved dropouts will be modeled by known measurements from retrieved dropouts (ie, participants who remain in the study after treatment discontinuation) in the same treatment group. If the number of retrieved dropouts is such that the model convergence is questionable and the

given parameter estimates cannot be obtained, then missing data at the Day 84 assessment will be estimated based on the placebo treatment group as described in subsequent sections of the SAP corresponding to the first sensitivity analysis.

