Supplemental analyses will be performed for the primary efficacy endpoint in order to assess any differences with the results from the primary analysis and investigate what effect, if any, protocol violations have on the trial results. In the first supplemental analysis, a mixed model for repeated measures (MMRM) approach will be utilized. The LDL-C values measured by preparative ultracentrifugation will be used. The analysis will include fixed effects for treatment group, visit, and treatment-by-visit interaction, along with covariates of the Baseline LDL-C value as a continuous covariate, CV risk (HeFH or non-HeFH), Baseline statin therapy (HIS or non-HIS). The restricted maximum likelihood estimation approach will be used with an unstructured covariance matrix. The LS mean, standard errors, and 2-sided 95% confidence intervals for the treatment group and for the comparison of the treatment group to the placebo group will be provided. The MMRM approach will include all available assessments of percent change in LDL-C from Day 1, Day 30, Day 84, Day 180, Day 270, and Day 365. The model assumes that the data are missing at random (MAR). If any data are missing, the model will use all information from the other time points to estimate the mean treatment difference at the given time point. No imputation of missing data will be performed. The analysis will be conducted for ITT Population.

The analysis will be implemented using SAS® Proc Mixed. The sample SAS code can be found below:

Note:

USUBJID = unique subject identifier
TREATMENT = 0 (Placebo), 1 (Obicetrapib)
VISIT = visit
LDLC_BASE = Baseline LDL_C value
PCHG = Percent change from Baseline
CVRISK = 1 (HeFH), 0 (non-HeFH)
STATIN = 1 (HIS), 0 (non-HIS)

```
proc mixed;
  class USUBJID TREATMENT VISIT CVRISK STATIN;
  model PCHG = TREATMENT LDLC_BASE CVRISK STATIN VISIT TREATMENT*VISIT / solution cl;
  Repeated VISIT / TYPE=UN sub=USUBJID;
  lsmeans VISIT*TREATMENT / cl diff;
```

run;

Additional supplementary analysis will be performed using the ANCOVA model from the primary analysis based on the FAS, MITT, MITT On Treatment, and PP populations. No imputation for missing data will be performed for the analysis.

Secondary Estimand

A secondary estimand will be assessed for the primary efficacy endpoint. The secondary estimand is defined by the following key attributes:

- **Treatment:** obicetrapib versus placebo
- **Target Population:** participants who are randomized into the study

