3.4.4 Subgroup Analysis

The primary efficacy endpoints also will be analyzed by the following subgroups:

- Age categories (<65 years, 65 to 74 years, and 75+ years)
- Sex (male, female)
- Race (white, Asian, Black or African American, Other)
- Ethnicity (Hispanic/Latino, Not Hispanic/Latino)
- BMI (<25 kg/m², 25 -30 kg/m², ≥30 kg/m²)
- Region (Asia, Eastern Europe, Western Europe and North America)
- Country (USA vs Other, Japan vs Other, China vs Other)
- Diabetes (yes, no)
- HDL-C (<40mg/dL, 40 - <60 mg/dL, ≥60mg/dL)
- ApoB (<60mg/dL, 60 - <90 mg/dL, ≥90mg/dL)
- ApoA1 (<110 mg/dL, ≥110 and <125 mg/dL, ≥125mg/dL)

- Lipoprotein(a) (<75nmol/L, ≥ 75 and <125 nmol/L, ≥ 125 nmol/L)
- Non-HDL-C (<100 mg/dL, ≥ 100 and <130 mg/dL, ≥ 130 mg/dL)
- LDL-C (<70mg/dL, ≥ 70 and <100 mg/dL, ≥ 100 mg/dL)
- TG (<150 mg/dL, ≥ 150 mg/dL)
- HbA1c (<5.7%, ≥ 5.7 to ≤ 6.4 %, >6.4 %)
- Urinary albumin:creatinine ratio (normal, micro-albuminuria, macro-albuminuria)
- eGFR (<30ml/min/1.73 m², ≥ 30 to <45ml/min/1.73 m², ≥ 45 to <60ml/min/1.73 m², ≥ 60 to <90ml/min/1.73 m², ≥ 90 ml/min/1.73 m²)
- Statin treatment (high dose, low or moderate dose, none)
- Ezetimibe use (yes, no)
- GLP1 use (yes, no)
- SGLT2 use (yes, no)
- Hs-CRP (<2mg/dL, ≥ 2 mg/dL)
- HeFH (Genotyping confirmed or DLCN>8 points or Simon Broome definite; Simon Broome possible FH diagnosis).

The ANCOVA model with fixed effects for the treatment group, subgroup variable, treatment-by-subgroup variable, along with CV risk (HeFH or non-HeFH) and Baseline statin therapy (HIS or non-HIS) and covariates of Baseline LDL-C will be used. The CV risk and Baseline statin therapy covariates may be excluded from the model in cases where inclusion causes the model not to converge. The least squares (LS) mean, standard errors, and 2-sided 95% confidence intervals for each treatment group and for the mean difference compared to placebo, within each level of the subgroup, will be estimated. No imputation of missing data will be performed; therefore, the subgroup analysis will perform using only observed data. For the primary efficacy endpoint, the LDL-C values measured by preparative ultracentrifugation will be used. However, if the analysis for the primary efficacy endpoint specified above will show a difference between the 3 LDL-C approaches, then Friedewald and Martin-Hopkins equations may be considered for subgroup analysis.

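### Subgroup CIs come from a joint model with no residual variance by level, and separately the MMRM shares one covariance matrix across arms; both can mis-size standard errors

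*SAP*

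**What the plan says.** **Primary model (SAP 3.4.1).** "The primary efficacy endpoint is the percentage change from Baseline to Day 84 in LDL-C" in the obicetrapib group compared with placebo. On variance: "The model will be fit assuming unequal variances for each treatment group". The sample code matches this: its `repeated` statement carries `group=TREATMENT`, which is one residual variance per arm.

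**Subgroups (SAP 3.4.4).** The section specifies "The ANCOVA model with fixed effects for the treatment group, subgroup variable, treatment-by-subgroup variable", together with CV risk, Baseline statin therapy and Baseline LDL-C. It asks for LS means and 95% CIs within each level, on observed data only. It gives no residual variance structure and no code. The list includes Baseline LDL-C (<70, 70 to <100, ≥100 mg/dL), non-HDL-C and ApoB.

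**MMRM (SAP 3.4.1, Supplemental Analyses).** "The restricted maximum likelihood estimation approach will be used with an unstructured covariance matrix". The sample code has `type=un` and no `group=` option, so both arms share one matrix. The Secondary Estimand (hypothetical strategy) uses a similar MMRM.

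**Design figures (SAP 2.2.1 and 2.2.2).** "Approximately 2400 eligible participants will be randomized in a 2:1 ratio"; "Assuming an approximate 5% drop out rate, approximately 2280 participants will be evaluable for efficacy"; "more than 90% power to detect a 30% reduction of LDL-C (standard deviation 15%) levels" "at a 1-sided significance level of 0.025".

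**The concern.** There are two separate points.

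1. Percent change divides by the participant's own Baseline. Unless variation in mg/dL scales exactly with LDL-C, the SD of percent change is larger at low Baseline. Protocol inclusion criterion 5 admits LDL-C from 55 mg/dL (lower still through the non-HDL-C route) with no upper cap, so the denominator varies widely. Subgroups cut on Baseline LDL-C sort participants by that denominator; non-HDL-C and ApoB probably come close to doing so. A joint model with at most one variance per arm averages over levels. It understates uncertainty in the lowest level and overstates it in the highest. At stake are the interval printed for LDL-C <70 mg/dL and any reading of whether the effect differs by Baseline LDL-C.

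2. The MMRM drops the by-arm variance that the primary analysis adopts. With unequal allocation, a shared variance mis-sizes the SE of the treatment difference whenever the arms' SDs differ. At stake is the CI for the supplemental analysis and for the hypothetical estimand.

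**Working it through.** **The plan's own figure.** 2400 × 0.95 = 2280, which at 2:1 is 760 placebo and 1520 obicetrapib. SE = 15 × √(1/760 + 1/1520) = 0.67, so 30 points is about 45 SEs. The stated power of more than 90% is reproduced and is in effect 100%. The documents state no subgroup CI width or coverage, so there is nothing on the disputed point to reproduce.

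**What has to be assumed.** The Baseline LDL-C distribution, the share below 70 mg/dL, the SD by level and the SD by arm. The documents give one SD, 15%.

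**Why the denominator matters.** A fixed 13.5 mg/dL is 13.5/60 = 22.5% at Baseline 60 and 13.5/130 = 10.4% at Baseline 130.

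**Subgroups, closed form.** Let the low level be a share s of participants with SD equal to R times that of the other levels, with the same R in each arm. The averaged variance is p = sR² + (1 − s). Reported/true SE is √p / R in the low level and √p elsewhere. Coverage is 2Φ(1.96 × ratio) − 1. Example, s = 0.2 and R = 1.5: p = 0.45 + 0.80 = 1.25, ratio = 1.118/1.5 = 0.745, coverage 85.6%.

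| s | R = 1.25 | R = 1.5 | R = 2 |
|---|---|---|---|
| 0.1 | 0.822 (89.3%) | 0.707 (83.4%) | 0.570 (73.6%) |
| 0.2 | 0.844 (90.2%) | 0.745 (85.6%) | 0.632 (78.5%) |
| 0.3 | 0.865 (91.0%) | 0.782 (87.5%) | 0.689 (82.3%) |

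At R = 1 there is no loss. Over this grid the other levels are too wide, by a factor of 1.03 to 1.38. With overall SD 15 and s = 0.2 (n = 456), the reported half-width is 1.96 × 15 × √(1/152 + 1/304) = 2.9 points. The true value is 3.9 at R = 1.5 and 4.6 at R = 2.

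**Subgroups, simulation.** 1500 trials per scenario; 2280 participants at 2:1; true effect −30 in every level; overall SD 15-16%; lognormal Baseline with median 92. The joint ANCOVA was given one residual variance per arm, which is the favourable reading of 3.4.4.

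| Residual variation | Coverage, <70 | Reported/true SE, <70 | Reported/true SE, ≥100 |
|---|---|---|---|
| 15%, proportional | 95% | 1.00 | 1.00 |
| 8 mg/dL + 12% | 89% | 0.84 | 1.12 |
| 11 mg/dL + 9% | 87% | 0.76 | 1.26 |
| 13.5 mg/dL, additive | 82% | 0.69 | 1.47 |

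Separately programmed repeats gave 95%, 90-91%, 87% and 83-84% below 70 mg/dL. In one of them, a variance for each arm and level restored coverage to 94-96%. Its reported half-width was about 3.5 points; with SE ratios of 0.83 to 0.70 in the three non-proportional scenarios, 3.5/0.83 = 4.2 to 3.5/0.70 = 5.0 is needed.

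A harsher model (600 runs per scenario) also put visit-to-visit error in the Baseline value; about 15% of participants fell below 70. Coverage there was 78%, 84% and 92% with by-arm variance (constant, mixed and proportional error) and 96%, 94% and 95% with variance by arm and level. That coverage is taken around each scenario's own mean estimate, which was −32.6 to −33.7 below 70. A variance option does not remove that shift.

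**MMRM, two-sample approximation.** With n on placebo, 2n on obicetrapib and r = obicetrapib SD / placebo SD, the pooled variance is (2r² + 1)/3. Reported variance of the difference: (2r² + 1)/3 × 1.5/n = (r² + 0.5)/n. True variance: (r²/2 + 1)/n. The ratio of SEs is √[(r² + 0.5)/(r²/2 + 1)].

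| r | Reported/true SE | Coverage |
|---|---|---|
| 0.67 | 0.88 | 91.5% |
| 0.8 | 0.93 | 93.1% |
| 1.25 | 1.08 | 96.5% |
| 1.5 | 1.14 | 97.4% |

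**The case against.** **Section 3.4.4 never says that variance is pooled.** True: that reading is partly an inference from silence. What stands is that nothing in the SAP provides variance by level. Nor is inheritance of the by-arm structure safe to assume: SAP 3.5.7 asks for unequal variances in the ABPM model, while the Appendix D code has no `group=` option.

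**A reader might infer that the departure from the primary model causes the subgroup problem.** It does not. The primary model separates variance by arm only, and the main simulation already uses that structure. Carrying it over would not cure the <70 interval.

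**A reader might infer that the MMRM narrows the subgroup CIs.** It cannot, because 3.4.4 uses ANCOVA. The MMRM error is modest, can go either way, and is computed from a two-sample approximation.

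**A reader might infer a breached error rate for the interaction.** The SAP includes the term but states no interaction test, p-value or alpha. In one simulation a nominal 5% test rejected 5%, 8%, 8% and 12% of the time without true heterogeneity. That matters only if such a p-value is reported.

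**The size is assumed and the setting is supportive.** Subgroups lie outside the sequential testing. Three of the 24 subgroup variables are tied to the denominator here; the rest may be little affected. All of this stands and limits the weight of the point. The provision in 3.4.1 for supportive analyses when assumptions fail concerns the primary analysis and does not expressly reach the subgroups.

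**Variance by level is not free for every subgroup.** Also true. eGFR has five levels, hence 10 variances, and <30 should be nearly empty because entry requires at least 30 at Screening.

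**Conclusion.** Both points hold as cheap improvements to the models as written.

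For subgroups defined by Baseline LDL-C, and likely non-HDL-C and ApoB, the CI would be too narrow in the lowest level and too wide in the highest unless variation is purely proportional. Coverage below 70 mg/dL is about 95% in that best case and falls to about 82-84% if variation is purely additive. These figures rest on an assumed Baseline distribution and assumed error structures. The model with error in Baseline as well gives 78-92%.

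It would go too far to say that subgroup CIs in general are far too narrow: the error runs both ways, and its size depends on SDs and shares that the documents do not give. Against an assumed 30-point effect and half-widths of a few points, no conclusion on direction changes. What suffers is the precision shown and the comparison across levels.

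For the MMRM, reported/true SE is about 0.88 to 1.14 over SD ratios of 0.67 to 1.5, with no error if the arms' SDs are equal.

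**What to change.** **Section 3.4.4.** State the variance structure. For Baseline LDL-C, non-HDL-C and ApoB, and for other subgroups where level sizes allow, use `repeated / group=TREATMENT*SUBGROUP` with `ddfm=satterth`. Alternatively, fit the observed-case ANCOVA within each level, dropping covariates that are constant there (such as CV risk within HeFH levels). Name the fallback in advance: `group=TREATMENT` where levels are sparse, such as eGFR <30. If an interaction p-value will be shown, say so and use the same variance grouping.

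**MMRM in 3.4.1, including the Secondary Estimand.** Use `repeated VISIT / type=un sub=USUBJID group=TREATMENT` with Satterthwaite or Kenward-Roger degrees of freedom, or justify a common matrix.

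**Cost.** Code options and a few SAP sentences, settled before unblinding so that the choice is not post hoc. The downside is more variance parameters and slightly wider CIs in small levels. With five post-Baseline visits an unstructured matrix has 5 × 6/2 = 15 parameters, so grouping by arm makes 30. The supplemental MMRM is specified on ultracentrifugation values, which at Days 30, 180 and 270 exist only when the triglyceride or low LDL-C trigger is met. A by-arm matrix may therefore be thin at those visits, and a fallback such as a common matrix with robust standard errors should be named.

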3.5 Safety Assessment

Safety Population will be the primary population for the safety analyses. All safety endpoints will be summarized descriptively by treatment group and overall. No statistical inference will be applied to the safety endpoints.

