## 8.9.1 Blood Pressure Monitoring

Blood pressure specifically will be measured using the following standardized procedures:

- Participants should be seated for at least 5 minutes in the examination room with the back supported, feet flat on the floor, and the measurement arm supported so that the midpoint of the manometer cuff is at heart level;
- An appropriately sized cuff should be used with the bladder centered over the brachial artery;
- The cuff size and arm used for the measurement should be recorded; the same arm should be used for all readings;
- Three seated blood pressure measurements (each measurement 1 to 2 minutes apart) should be obtained using the same arm at each site visit. Mean seated blood pressure is defined as the average of 3 seated blood pressure measurements at a single site visit; and
- If the lowest and highest blood pressure measurements are >15 mmHg apart, additional readings should be performed.

Blood pressure readings, both systolic and diastolic, will be evaluated over time by the independent DSMB, who will monitor unblinded safety data during the study on a bi-annual basis (ie, approximately every 6 months). Changes in blood pressure, as well as heart rate, will be compared between treatment groups with respect to mean and median values over time using both actual values and absolute changes from Baseline. In addition, treatment groups will be compared with respect to the incidence of hypertensive status and other vital sign abnormalities as defined in the SAP.

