#### 9.2.2 Analysis of Safety

The Safety Population will be the primary population for the safety analysis. All safety endpoints will be summarized descriptively.

AEs will be categorized by primary system organ class and preferred term as coded using the Medical Dictionary for Regulatory Activities category designations. Summaries of AEs, including the number and percentage of participants who experience an AE, will be provided.

Laboratory values will be summarized descriptively, including the change from Baseline, by treatment group, and overall. In addition, shift tables will be presented to describe the change in laboratory parameter values at post-Baseline visits using normal range categories (low, normal, and high).

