3.1.5 Summary Statistics

Categorical data will generally be summarized with counts and percentages of subjects. The denominator used for the percentage calculation will be clearly defined. Continuous data will generally be summarized with descriptive statistics including n (number of non-missing values), mean, median, standard deviation, 1st and 3rd quartiles, minimum, and maximum.

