Cases of macular degeneration will be recorded and summarized using the appropriate system organ class. These events will be summarized by severity and relationship to study drug for each treatment group.

3.5.3 *Clinical Laboratory Tests*

Blood and urine samples for clinical laboratory evaluations (including a full serum chemistry panel, hematology, coagulation, and urine dipstick analysis) will be collected at visits specified in Table 1. Only urine dipstick analysis will be performed locally, while the rest of clinical laboratory test will be processed by a central laboratory. See Appendix A of the protocol for a complete list of analytes. Blood samples (a full serum chemistry panel, hematology, coagulation) must be collected under fasting conditions (a minimum of 8 hours) and prior to the next dose of study drug (at applicable visits).

Laboratory values will be summarized descriptively, including the change from baseline. In addition, shift tables for select parameters will be presented to describe the change in laboratory parameter values at post-baseline visits using normal range categories (low, normal, and high).

Chemistry and hematology laboratory parameters will be listed.

3.5.4 *Vital Signs*

Vital signs (heart rate and blood pressure) measured in triplicate prior to study administration at applicable visits as indicated in [Table 1](#). Values will be summarized with descriptive statistics, including the change from baseline at each visit by treatment group and overall.

Additional summaries of blood pressure measurements will be performed, within treatment group and time point, using counts of triplicate means that meet the following criteria:

- Systolic blood pressure:
 - ≥ 160 mmHg
 - ≥ 180 mmHg
 - change from baseline by ≥ 20 mmHg
- Diastolic blood pressure:
 - ≥ 100 mmHg
 - ≥ 110 mmHg
 - change from baseline by ≥ 15 mmHg.

Vital signs will be listed.

3.5.5 *Electrocardiograms*

A single 12-lead ECG will be performed at Visit 2 and Visit 7/EOT/ET and will be read locally.

ECG parameters will be recorded as normal, abnormal or not done. Abnormal values will be assessed as clinically significant or not clinically significant. Counts and percentages for ECG parameters will be summarized by treatment group and in total.

3.5.6 *Physical Examinations*

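### No between-group difference or confidence interval is planned for office blood pressure and heart rate, and the SAP's bar on safety inference contradicts its own ABPM test

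*SAP*

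**What the plan says.** **Collection.** Protocol 8.9.1: "Three seated blood pressure measurements (each measurement 1 to 2 minutes apart) should be obtained using the same arm at each site visit". Protocol 8.9 applies triplicate measurement to heart rate as well, and the Schedule of Procedures marks vital signs at every visit from V1 to V8.

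**Comparison in the protocol.** Section 8.9.1: "Changes in blood pressure, as well as heart rate, will be compared between treatment groups with respect to mean and median values over time". It adds that "treatment groups will be compared with respect to the incidence of hypertensive status and other vital sign abnormalities as defined in the SAP". Section 9.2.2, however, says: "All safety endpoints will be summarized descriptively".

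**Analysis in the SAP.** Section 3.5 says: "No statistical inference will be applied to the safety endpoints". Section 3.5.4 (Vital Signs) covers office readings in two steps. First: "Values will be summarized with descriptive statistics, including the change from baseline at each visit by treatment group and overall". Then it summarises blood pressure "within treatment group and time point, using counts of triplicate means that meet the following criteria", the criteria being SBP at or above 160 and 180 mmHg, DBP at or above 100 and 110 mmHg, and rises of at least 20 (SBP) or 15 (DBP) mmHg. It gives no model, no between-arm difference and no interval. The term hypertensive status, which the protocol leaves to the SAP, does not appear there.

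**ABPM.** SAP 2.3.4 lists ABPM as a safety endpoint. SAP 3.1.6 states a hypothesis for it with a 3 mmHg margin. SAP 3.5.7 fits an ANCOVA and decides non-inferiority from the upper limit of a 2-sided 95% CI.

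**Declared changes.** SAP section 6 lists three changes from the protocol: extra trough time points, extra cardiovascular endpoints and subgroup analyses. Office vital signs are not among them.

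**The concern.** The plan takes a possible pressor effect seriously. There is an event of special interest for changes in antihypertensive treatment, DSMB review of blood pressure, and a dedicated ABPM substudy. Yet the largest blood pressure data set in the trial, office readings from all participants at each visit, is carried only to side-by-side summaries. A reader of the study report would see two columns of means and would have to work out the treatment difference and its uncertainty unaided, without adjustment for Baseline or the stratification factors.

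The SAP also contradicts itself. Read literally, SAP 3.5 forbids the ABPM test that SAP 3.5.7 specifies. Whoever programs or reviews the analysis should not have to decide which sentence governs.

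**Working it through.** **1. The texts side by side**

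| Item | Protocol | SAP |
|---|---|---|
| Office BP and heart rate, continuous | 8.9.1: compared between groups on means and medians | 3.5.4: descriptive values and change, by arm and visit |
| Office BP, categorical | 8.9.1: incidence compared, definition left to the SAP | 3.5.4: counts against listed thresholds; term not defined |
| Safety in general | 9.2.2: descriptive | 3.5: descriptive, no inference |
| ABPM (a safety endpoint) | 9.2.6.1: non-inferiority | 3.1.6 and 3.5.7: test and CI, against 3.5 |

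The SAP plans no between-arm estimate for the first two rows. The last two rows conflict within the SAP.

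**2. The plan's own ABPM figure**

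Inputs (Protocol 9.2.6.1): N about 200, margin 3 mmHg, true difference 0, SD 8 mmHg, 1-sided 0.05. Allocation is 2:1, so 200/3 on placebo and 400/3 on obicetrapib.

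- SE = 8 × √(3/200 + 3/400) = 8 × 0.15 = 1.20 mmHg
- Power at 1-sided 0.05 = Φ(3/1.20 − 1.645) = Φ(0.855) = 80.4%, which reproduces the stated figure of more than 80%.
- Power under the SAP 3.5.7 rule (1-sided 0.025) = Φ(2.50 − 1.96) = Φ(0.54) = 70.5%.
- 95% CI half-width = 1.96 × 1.20 = 2.35 mmHg.

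The half-width assumes that all 200 are analysed. The primary ABPM population (SAP 3.2.7) also requires valid recordings at Baseline and Day 270 and 80% to 120% compliance, so the number analysed may be smaller.

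**3. An office SBP difference**

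Inputs: 2400 × 0.95 = 2280 (Protocol 9.2.6), split 1520 and 760. The documents give no SD for office SBP change, so 12 to 18 mmHg is assumed.

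SE = SD × √(1/1520 + 1/760) = SD × 0.0444

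| Assumed SD (mmHg) | SE (mmHg) | 95% half-width (mmHg) |
|---|---|---|
| 12 | 0.53 | 1.04 |
| 15 | 0.67 | 1.31 |
| 18 | 0.80 | 1.57 |

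The figure of 2280 is the protocol's number evaluable for efficacy. With all 2400 (1600 and 800) the half-widths are 1.02, 1.27 and 1.53 mmHg.

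Break-even: the office SE equals the ABPM SE when SD = 1.20/0.0444, about 27 mmHg. Below that, the office difference is the more precise of the two.

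**4. Threshold crossings**

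The half-width of a risk difference at 2280, with the same assumed incidence in both arms, is 1.96 × √[p(1 − p)(1/1520 + 1/760)]. This gives 0.87 percentage points at 1%, 1.22 at 2%, 1.90 at 5% and 2.61 at 10%.

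**The case against.** The strongest defence is that the SAP does what the protocol asks. Protocol 9.2.2 is descriptive for all safety endpoints. Section 8.9.1 names no test, model or interval, and tabulating means and medians by arm is a comparison of a kind. Its sentence also follows the one on DSMB review, so it could be describing monitoring. Much of this stands: the SAP cannot be called a plain departure. Against the monitoring reading, 8.9.1 refers to definitions in the SAP, whereas DSMB procedures are left to the DSMB Charter.

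Three stronger readings are tempting, and the documents do not support them.

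- *A reader might infer that office blood pressure is reduced to raw counts, which 2:1 allocation would double in the obicetrapib arm at equal risk.* SAP 3.5.4 also summarises change from baseline, and SAP 3.1.5 sets a default: "Categorical data will generally be summarized with counts and percentages of subjects". Protocol 9.2 likewise requires percentages. Section 3.5.4 could state the denominator more clearly, but an incidence can be reported under the existing rules.
- *A reader might infer that a blood pressure effect is never estimated.* ABPM gives an adjusted between-arm difference with a 95% CI for 24-hour, daytime and nighttime SBP, and for DBP. Blood-pressure-driven changes in antihypertensive treatment are tabulated as number and percentage by arm.
- *A reader might infer that blood pressure is the harm the plan ranks first.* The DSMB text names it together with the events of special interest and ranks neither.

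Two further points are fair. The missing label may be only a label, since SAP 3.5.4 lists usable thresholds. And an unadjusted difference can be worked out from n, mean and SD by arm. That is a reason to report the difference properly, with Baseline adjustment.

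**Conclusion.** The point holds in a limited form. For office blood pressure and heart rate the SAP plans no between-group difference or interval, although Protocol 8.9.1 uses comparative language, and section 6 is silent on it. Separately, the sentence in SAP 3.5 contradicts the ABPM hypothesis and decision rule and needs correcting however 8.9.1 is read.

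The planned between-arm blood pressure estimates rest on about 200 consenting participants at selected sites and one post-baseline time point, with a half-width of about 2.35 mmHg at SD 8. Office SBP in about 2280 would give about 1.0 to 1.6 mmHg at every visit, on an assumed SD of 12 to 18 mmHg. The ordering does not depend on that range, since it reverses only above an SD of about 27 mmHg. Office and ambulatory pressure are different measures, so the office estimate would complement ABPM and would not replace it.

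This is an improvement that should be made. It is not a flaw that invalidates the safety analysis.

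**What to change.** 1. **SAP 3.5:** exempt the ABPM analyses and the estimation of office blood pressure and heart rate differences from the no-inference sentence.
2. **SAP 3.5.4, continuous:** add one repeated-measures model (or ANCOVA) for each of SBP, DBP and heart rate on the Safety Population, adjusted for the Baseline value and the two stratification factors. Report the obicetrapib minus placebo difference with a 95% CI by visit, labelled as safety estimation without multiplicity adjustment and without a formal test.
3. **SAP 3.5.4, categorical:** report the thresholds already listed as n/N (%), with a risk difference and 95% CI for any post-baseline visit. State that these criteria are what the protocol means by hypertensive status.
4. **SAP section 6:** record the change.

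The cost is SAP wording and some added tables, with no new data and no change to clinical management. The statistical price is more unadjusted intervals: three variables at six post-baseline visits (V3 to V8) give 18, and six thresholds give 6 more, 24 in all. Limiting the threshold intervals to any post-baseline visit keeps that number down. Adding each of the six visits would bring 36 more.
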